## **7.2. STUDY PROCEDURES AND EVALUATION SCHEDULE**

Table 2 summarizes the study procedures and evaluation schedule.

**Table 2. Schedule of Events**

Time Points a /Procedures	Prior to Treatment Period		Treatment Period			Regression Period	
	Visit 1	Visit 2	Visit 3	Visit 4	Visit 5	Visit 6	
	Screening b	Baseline (Week 0)	Week 1 (± 2 days)	Week 4 (± 3 days)	Week 12 (± 3 days)	Week 24 (± 3 days)	
ICD with HIPAA disclosure & photograph release	X						
Collect demographics (including Fitzpatrick skin type and oiliness level), general medical history, & concomitant medications	X						
Interview for compliance		X*	X	X	X	X	
15-minute acclimation	X	X	X	X	X	X	
Clinical and subjective evaluations of efficacy ██████████	X d	X	X	X	X	X	
Review of eligibility	X						
Subject qualification by PI	X						
Enrollment & randomization	X						
██████████			█	█	█	█	
██████████		█	█	█	█	█	
IP and auxiliary product dispensed (as applicable) with subject instructions and daily diary e	X Auxiliary products; Appendix VI instructions; daily diary	X IP starter kit & auxiliary products; Appendix VII instructions		X IP refill kit & auxiliary products; Appendix VII instructions	X Auxiliary products; Appendix X instructions		
Daily diary reviewed		X	X	X	X	X	
IP/auxiliary product checked for use compliance (as applicable)		X	X	X	X	X	
IP/auxiliary product and daily diary collected					X All IPs	X Auxiliary products and daily diary	
Collect/record AEs and changes in health/medications	X* AEs only	X	X	X	X	X	
Subject disposition						X f	

aSee section 7.1 regarding possible separation of Visits 2-6 into sub-visits.

bScreening will occur up to 10 days prior to Baseline (or Visit 2A, as applicable). If Visit 2 (or Visit 2A) immediately follows Screening (on the same day), the denoted (\*) AE collection and interview for compliance (for Visit 2 or Visit 2A, as applicable) may be waived. All Visit 1 procedures must be completed prior to Visit 2 commencing.

cThe efficacy ██████████ evaluations will be conducted independently by each of three Expert Graders (except at Screeningd), but only the PI will question the subject for the subjective parameters.

dOnly the "mottled hyperpigmentation" and "global wrinkling" parameters will be conducted at Screening as part of the eligibility review. The evaluations will be conducted only by the PI.

eAdditional IP, auxiliary product, and daily diary units may be dispensed as needed/previous units collected at the Site's discretion.

fSubject disposition will be recorded at final study visit or at the time of subject discontinuation from the study.

### **7.2.1. Recruiting**

Candidate subjects will be recruited using IRB-approved materials. Interested candidates will be scheduled for Visit 1.

### **7.2.2. Visit 1 (Screening)**

Selected candidates will report to the test facility. On the day of the study visit, candidate subjects should remove all leave-on facial products (including eye makeup) and arrive at the visit with a clean face. Note: if a candidate subject arrives with facial products on, she may remove the facial products and wash her face with a non-medicated cleanser on-site prior to the acclimation period. This will not be recorded as a deviation. Candidate subjects will take part in the following procedures:

#### **7.2.2.1. Informed Consent**

Informed consent will be obtained as described in section 4.1. The ICD will include a HIPAA disclosure. Subjects will also review and sign a Photograph Release. Subjects who sign the ICD and Photograph Release will be sequentially assigned a Subject ID (see section 6.6).

#### **7.2.2.2. Acclimation**

Subjects will acclimate to conditions in the facility for at least 15 minutes before the clinical evaluations of eligibility (see section 7.2.2.3) are conducted.

#### **7.2.2.3. Medical History, Concomitant Medications, and Review of Eligibility**

The demographics (including Fitzpatrick skin type [Appendix I] and oiliness level [Appendix II]), medical history, and concomitant medications of each candidate subject will be collected and reviewed (this interview may occur during the acclimation period).

All of the eligibility requirements of the study will also be reviewed to assess each candidate subject's eligibility. As part of this review, the "mottled hyperpigmentation" and "global wrinkling" clinical evaluations will be conducted by the PI as described in section 7.2.3.3.1 after the acclimation period is completed in order to determine if the individual meets the eligibility requirements (see inclusion criteria [d] and [e] in section 4.2.1). In addition, the PI or designee will review each subject's facial products to ensure the subject meets the eligibility criteria (see exclusion criterion [h] in 4.2.2) and approve/record each subject's regular facial products that she will continue to use during the study (see section 4.3).

The PI will review the above information (medical history, concomitant medications, and eligibility review) to confirm the eligibility of each subject prior to their enrollment in the study.

#### **7.2.2.4. Enrollment and Randomization**

Upon enrollment, each subject will be assigned a randomization number (see section 6.6).

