DOSE AND MODE OF APPLICATION	
At Screening (Visit 1), each subject will be provided with an auxiliary cleanser and an auxiliary moisturizer to use full-face for the duration of the study. Each subject will be instructed to wash her face twice daily (morning and evening) with the AM & PM Cleanser. In the morning after washing, subjects will apply the AM Moisturizer full-face (the AM Moisturizer may be used again in the evening [after completing the mask treatment, as applicable], if desired).
 
At Baseline (Visit 2), each subject will be randomly assigned to also use either the active or sham PM Mask Treatment (with respective Mask Activator) for the 12-week treatment period of the study. In the evening after washing, subjects will use the PM Mask Treatment (either active or sham) for 10 minutes.
 
A 12-week regression period will begin at Week 12 (Visit 5); during the regression period, subjects will continue using the auxiliary products as described previously, but there will be no mask usage.
				
STUDY DURATION	
The study will consist of 6 visits* over 24 weeks with visits scheduled at Screening (Visit 1, up to 10 days prior to Baseline), Baseline (Week 0; Visit 2), Week 1 (Visit 3), Week 4 (Visit 4), Week 12 (Visit 5), and Week 24 (Visit 6). Baseline to Week 12 (Visit 2 to Visit 5) will comprise a 12-week treatment period, and Week 12 to Week 24 (Visit 5 to Visit 6) will comprise a 12-week regression period.
 
*If required for scheduling, Visits 2-6 may each be separated into up to three sub-visits (e.g. Visit 2A, 2B, and 2C) such that the imaging and subject questionnaire will occur separately from the clinical and subjective evaluations of efficacy and tolerance (which may themselves be conducted by different Expert Graders at different sub-visits, as needed). See section 7.1 for details.
				
METHODOLOGY	
 
Clinical evaluations of efficacy: fine lines, periorbital wrinkles, global wrinkling, surface roughness, uneven skin tone, mottled
 
				

	
hyperpigmentation, sallowness or yellowing, lack of radiance, [REDACTED]
 
 
• [REDACTED]
 

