## **3. STUDY DESIGN**

This is a single-center, 2-cell, sham-controlled, randomized, evaluator-blinded clinical usage study utilizing three Expert Graders (i.e. the PI plus two additional board-certified dermatologist Expert Graders; see Appendix XI). Up to approximately 125 subjects will be enrolled to finish with at least 96 subjects (targeting 48 subjects per cell). The target population is 35- to 70-year-old females with mild to moderate mottled hyperpigmentation on the face and moderate to severe facial wrinkles. Enrollment will be evenly distributed across all Fitzpatrick skin types (i.e. an approximately equal number of subjects will be enrolled per skin type per cell).

Subjects will be assessed at Screening, Baseline (Week 0), Week 1, Week 4, Week 12, and Week 24, as described in section 7.

At Screening (Visit 1), each subject will be provided with an auxiliary cleanser (twice daily usage – morning and evening) and an auxiliary moisturizer (once daily usage in the morning after cleansing [plus additional evening usage (after completing the mask treatment, as applicable), as desired]) to use full-face for the duration of the study. At Baseline (Visit 2), each subject will be randomly assigned to also use either the

active or sham light therapy mask (with respective activator; once daily usage for 10 minutes in the evening after cleansing) for the 12-week treatment period of the study. The active and sham masks will be identical in appearance; the Expert Graders will be blind to the IP assignment, and subjects will also be blinded to the extent possible (see section 6.6).

A 12-week regression period will begin at Week 12 (Visit 5); during the regression period, subjects will continue using the auxiliary products as described previously, but there will be no mask usage.

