## 6.6. RANDOMIZATION/IP ALLOCATION AND BLINDING

Subjects who sign the ICD will be sequentially assigned a Subject ID. The Subject ID will begin with the four-digit center ID (1001) followed by a unique four-digit subject identifier assigned in ascending order and beginning with "1001," resulting in an eight-digit Subject ID (e.g. "10011001," "10011002," etc.). Once a Subject ID has been assigned to a subject, it cannot be reassigned to another subject.

Enrollment in the study will be evenly distributed across all Fitzpatrick skin types. Six strata will be created, with one stratum for each of the six Fitzpatrick skin types. A randomization scheme will be performed separately for each stratum. Upon enrollment in the study, subjects will be allocated to one of the six strata based on their Fitzpatrick skin type. Within each stratum, subjects will then be randomly assigned to one of two treatment cells (Active or Sham). An extra stratum will be created to provide replacement kits as needed (e.g. if a subject misplaces or breaks the PM Mask Treatment in the starter kit) so that there will be a total of seven strata in the study. In the event of a replacement, the site should contact the Sponsor's Clinical Supplies department; subjects will be given a new randomization number from this stratum based on their original treatment assignment. Once a randomization number has been assigned to a subject, it cannot be reassigned to another subject. The randomization scheme will be devised by the Sponsor's Quantitative Sciences Department.

The randomization numbers will be incorporated into the IP labeling, as described in section 6.2.

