7.2.3.3.1. Efficacy

The PI and two other Expert Graders\* (see Appendix XI) will each separately assess each subject’s facial skin for the appearance of the following aging parameters using the applicable grading scales shown in Appendix IV:

- Fine lines
- Periorbital wrinkles
- Global wrinkling\*
- Surface roughness
- Uneven skin tone
- Mottled hyperpigmentation\*
- Sallowiness or yellowing
- Lack of radiance

■ [REDACTED]

*\*Note: At Visit 1, these evaluations will be conducted only by the PI. For enrollment at Visit 1 (see Inclusion Criteria [d] and [e] in section 5.2.1), an individual must have a score of 1-6 for the “mottled hyperpigmentation” parameter and a score of 4-9 for the “global wrinkling” parameter, as determined by the PI.*

[REDACTED]

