#### **7.2.3.5. IP Dispensing and Instructions**

Each subject will receive a starter kit for the randomly assigned product cell (see section 6). Additional auxiliary product will also be dispensed, as needed. The site designee will review the treatment period instructions (Appendix VII) with the subjects. If Visit 2 is split into sub-visits, subjects will be instructed to begin following the treatment period instructions only after completion of the final Visit 2 sub-visit.

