1.2 STUDY DESIGN

Extracted from the protocol:

This is a single-center, 2-cell, sham-controlled, randomized, evaluator-blinded clinical usage study utilizing three Expert Graders (i.e. the Principal Investigator [PI] plus two additional board-certified dermatologist Expert Graders; see Appendix XI). Up to approximately 125 subjects will be enrolled to finish with at least 96 subjects (targeting 48 subjects per cell). The target population is 35- to 70-year-old females with mild to moderate mottled hyperpigmentation on the face and moderate to severe facial wrinkles. Enrollment will be evenly distributed across all Fitzpatrick skin types (i.e. an approximately equal number of subjects will be enrolled per skin type per cell).

Subjects will be assessed at Screening, Baseline (Week 0), Week 1, Week 4, Week 12, and Week 24.

At Screening (Visit 1), each subject will be provided with an auxiliary cleanser (twice daily usage – morning and evening) and an auxiliary moisturizer (once daily usage in the morning after cleansing [plus additional evening usage (after completing the mask treatment, as applicable), as desired]) to use full-face for the duration of the study. At Baseline (Visit 2), each subject will be randomly assigned to also use either the active or sham light therapy mask (with respective activator; once daily usage for 10 minutes in the evening after cleansing) for the 12-week treatment period of the study. The active and sham masks will be identical in appearance; the Expert Graders will be blind to the IP assignment, and subjects will also be blinded to the extent possible (see section 6.6).

A 12-week regression period will begin at Week 12 (Visit 5); during the regression period, subjects will continue using the auxiliary products as described previously, but there will be no mask usage.

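### Does it matter that the protocol places randomization at both Visit 1 and Baseline (Visit 2)?

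*Protocol*

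**What the plan says.** **Text that points to Visit 1**

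- Protocol 7.2.2.4, under Visit 1 (Screening): "Upon enrollment, each subject will be assigned a randomization number".
- Protocol Table 2: the row "Enrollment & randomization" has a single mark, in the Screening column.
- Protocol 6.6: "Upon enrollment in the study, subjects will be allocated to one of the six strata based on their Fitzpatrick skin type", after which the cell is drawn within the stratum. This section names no visit. It reaches Visit 1 by inference, because 7.2.3.3.1 says "For enrollment at Visit 1 (see Inclusion Criteria [d] and [e] in section 5.2.1), an individual must have a score of 1-6" and 7.2.2.5 treats subjects as enrolled when the cleanser and moisturizer are dispensed at Visit 1.
- Protocol 7.2.3, the Visit 2 procedures, contains no randomization step. Section 7.2.3.5 only dispenses: "Each subject will receive a starter kit for the randomly assigned product cell (see section 6".

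**Text that points to Baseline**

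- Protocol synopsis: "At Baseline (Visit 2), each subject will be randomly assigned to also use either the active or sham PM Mask Treatment". Sections 3 and 6.5 carry the same sentence with small variations.
- SAP 1.2: "At Baseline (Visit 2), each subject will be randomly assigned to also use either the active or sham light therapy mask". The SAP marks this section as taken from the protocol, so it is a copy and not a second source.

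**The concern.** The time of randomization normally decides who belongs to the randomized population and whether allocation comes before or after the baseline measurement. With two times in current text, two analysts could count different people as randomized. Under the Visit 1 reading, allocation would also always precede the three graders' baseline scores, because 7.1 requires all Visit 1 procedures to be finished before Visit 2 starts, even on the same day. If knowledge of the cell could leak, or if early leavers differed by cell, baseline scores or analysis sets could be distorted.

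**Working it through.** **1. Can both statements be true?** One could suppose that the number is issued at Visit 1 and the cell is drawn at Visit 2. The documents rule this out. Section 6.2 supplies one starter kit and one refill kit per randomization number, and the disclosure envelopes in 6.6 are specific to the number. Whoever has a number has a cell, so the contradiction is real.

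**2. How far apart are the two times?** Section 7.1 allows Screening up to 10 days before Baseline, or on the same day, and lets a split Baseline run over 3 days.

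- Visit 1 to Baseline: 0 to 10 days.
- Visit 1 to the final Baseline sub-visit, after which mask use starts: at most 10 + 3 = 13 days.

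**3. Who changes status?** Only a subject who is enrolled at Visit 1 and leaves before being randomized at Visit 2.

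| Item | Rule | Visit 1 reading | Visit 2 reading |
|---|---|---|---|
| Full analysis set (SAP 3.1) | Used the product, with baseline and at least one later value | Out | Out |
| Safety set (SAP 3.3) | Randomized and used the product | Out | Out |
| Demographic and baseline tables (SAP 3.4) | All randomized | In | Out |
| EDC pages (protocol section 12) | Each randomized subject | In | Not in, except screen failures with an AE (4.5, 7.5.2, 10.3.1) |

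Anyone who uses a mask has reached Visit 2 and is randomized under both readings. The two sets that carry the efficacy and safety results therefore have the same members. SAP 6.4.1 compares baseline characteristics between cells, but no efficacy decision in SAP 6.2 depends on those tests.

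**4. Does power change?** Protocol 8.4 states 92% for 48 completers per cell, an effect of 0.7 and two-sided alpha 0.05. No standard deviation is given; 1 is assumed here, so that 0.7 is a standardized effect.

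- Normal approximation: 0.7 / √(2/48) = 0.7 × √24 = 3.43; 3.43 − 1.96 = 1.47; power = Φ(1.47) = 92.9%.
- Noncentral t with 94 degrees of freedom: 92.4%.
- If 0.7 is in scale points, the normal approximation gives 99.0% at a standard deviation of 0.8 and 81.5% at 1.2.

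The stated figure is reproduced. Its input is completers, so no value in this range depends on which visit is named.

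**5. Could allocation before baseline grading bias the comparison?** Under 6.6 the evaluators do not know the cell, and staff who dispense do not evaluate. The first cell-specific item, the starter kit, is dispensed at Visit 2 (Table 2, 7.2.3.5). Between the visits both cells use the same cleanser and moisturizer. A subject who leaves in that interval has no information about her cell, so her leaving cannot depend on it while the blind holds.

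**The case for a change.** The strongest case for a change is that timing of randomization should have one answer and that giving one is cheap. Under the Visit 1 reading, an early leaver enters the SAP 3.4 tables without the three graders' baseline scores. She also uses up a randomization number that 6.6 forbids reassigning, in a stratum that aims for only 8 completers per cell. Randomizing at Visit 2, after baseline grading, would avoid both and shorten the gap to first use.

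The inconsistency stands, and so does the possible difference of a few subjects in descriptive tables. The rest carries little weight:

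- A lost number costs little. Section 7.5.2 allows replacement with sponsor approval, and the ANCOVA, which includes skin type group, does not need equal cells.
- Early leavers are largely accounted for. Section 7.5.2 requires a logged reason for every consented subject who is not included or who discontinues, and its list already covers ineligibility found after enrollment, withdrawal and loss to follow-up. Screen failures with an adverse event are entered in the EDC system.
- Moving randomization to Visit 2 is a preference that the documents do not require, with no shown gain. It would create a group enrolled but not randomized, for whom a loss to follow-up would have no clear EDC route. It would also unsettle each statement that counts enrollment by skin type within cell (synopsis, section 3, inclusion criterion f, section 5, SAP 1.2), since these presume that an enrolled subject already has a cell.

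**Conclusion.** This is a clerical slip with no effect on the trial's conclusions. The step-by-step procedures give a workable sequence: number and cell at Visit 1, kit at Visit 2. The Baseline sentence reads naturally as a loose description of when subjects receive and start the assigned mask. An analyst can take as randomized everyone who was given a randomization number, and the SAP 3.4 tables are then defined without further text.

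The size is nil for the full analysis set, the safety set and power. For the demographic and baseline tables and some EDC records, it is the number of subjects lost in a window of at most 13 days, which the documents do not give. The conclusion rests on grader blinding working as 6.6 describes and on nothing cell-specific being handed out before Visit 2. Aligning the sentence would be harmless housekeeping if the documents were reissued for another reason, but it would alter no result.

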#### **7.2.2.5. Auxiliary Product Dispensing and Instructions**

Each enrolled subject will receive a unit of the auxiliary cleanser and the auxiliary moisturizer, along with a daily diary for the subject to record her product usage throughout the study (note: the Site may dispense/collect diary units at its discretion throughout the study). The site designee will review the subject instructions in Appendix VI with each subject. The subject instructions in Appendix VI contain the instructions relevant between Visit 1 and initiation of IP usage. Subjects will begin using the auxiliary products on the night of Visit 1.

#### **7.2.2.6. AE Collection**

Individuals that have signed the ICD will be questioned and assessed for AEs before leaving the facility. (Note: if Visit 2 or Visit 2A will occur on the same day as Visit 1, the Visit 1 AE collection may be waived).

#### **7.2.3. Visit 2 (Week 0, Baseline)**

On the day of the study visit, subjects should remove all leave-on facial products (including eye makeup) and wash with the provided facial cleanser prior to the visit. No other topical products should be applied to the face until the study visit has been completed. Note: if a subject does not follow these directions, she will be asked to remove her facial products and wash her face with the auxiliary cleanser on-site prior to the acclimation period (Note: this will not be considered a deviation). Subjects will take part in the following procedures:

##### **7.2.3.1. AE Collection & Interview for Compliance**

The PI or designee will interview the subjects to collect and record any AEs or changes to health/concomitant medications that may have occurred since the previous visit. Subjects will also be interviewed for compliance with study directions. (Note: this interview may be skipped at Visit 2 [or Visit 2A, as applicable] if Visit 1 occurred on the same day). This interview may occur during the acclimation period.

##### **7.2.3.2. Acclimation**

Subjects will acclimate to conditions in the facility for at least 15 minutes before the clinical and subjective evaluations of efficacy [REDACTED] are conducted.

**7.2.3.3. Clinical and Subjective Evaluations of Efficacy** [REDACTED]

The following evaluations will be conducted after the acclimation period:

[figure not shown]
7.2.3.3.1. Efficacy

The PI and two other Expert Graders\* (see Appendix XI) will each separately assess each subject’s facial skin for the appearance of the following aging parameters using the applicable grading scales shown in Appendix IV:

- Fine lines
- Periorbital wrinkles
- Global wrinkling\*
- Surface roughness
- Uneven skin tone
- Mottled hyperpigmentation\*
- Sallowiness or yellowing
- Lack of radiance

■ [REDACTED]

*\*Note: At Visit 1, these evaluations will be conducted only by the PI. For enrollment at Visit 1 (see Inclusion Criteria [d] and [e] in section 5.2.1), an individual must have a score of 1-6 for the “mottled hyperpigmentation” parameter and a score of 4-9 for the “global wrinkling” parameter, as determined by the PI.*

[REDACTED]

